Concerns about buprenorphine diversion are common, but data are lacking. Diversion, meaning that patients who are prescribed buprenorphine (including buprenorphine-naloxone) give or sell the medication to others who are not engaged in treatment is a major concern for prescribers and policy makers.⁴⁷⁻⁵⁰ Those taking diverted medication may be “self-treating” withdrawal symptoms, which is common among PWID, or seeking euphoric effects.^{48,51-56} Buprenorphine-naloxone is more commonly prescribed than buprenorphine alone, because the naloxone may reduce abuse potential.⁵⁷ Buprenorphine is a partial opioid agonist that is unlikely to cause euphoria among individuals with high levels of opioid tolerance when taken sublingually. However, it can be adulterated and injected for euphoric effects. The naloxone in the combination product is unabsorbed when taken sublingually, but it is more bioavailable if injected and will provide antagonism at opioid receptors.⁵⁸ Therefore, PWID are unlikely to seek diverted buprenorphine-naloxone to inject for euphoric effect; however, they could divert medication to others posing a public health risk.^{48,51,59} Making BMT available at SEPs, where there is active drug use, could increase risk of diversion; however, it could also address an unmet need for treatment. In 2013, we found that among 102 SEP participants, 57 had taken diverted buprenorphine, and this was most common among those with barriers to BMT.¹³ In focus groups, SEP participants directly reported that they took diverted buprenorphine due to insufficient access to BMT.⁵ Other studies have found inadequate BMT access as a risk factor for using diverted buprenorphine.^{51,60} *Therefore, onsite BMT at SEPs could also paradoxically reduce diversion.* There are also other important areas that require inquiry. Though 35-100% of BMT patients initiating treatment have reported taking diverted buprenorphine, estimates of how many BMT patients divert their own medication to illicit markets are limited.^{56,59,61,62} Among inmates enrolled in trials of BMT initiation prior to jail or prison release, 10-20% were removed from the trials for attempting to divert their medication;^{28,29} however, data relevant to community BMT patients are needed to inform clinical practice and policies regarding buprenorphine prescribing (e.g., establishing monitoring guidelines).

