Aim 1: Secondary outcomes (efficacy): a.) Illicit opioid use: We will check urine drug testing at each research visit and use the Addiction Severity Index (ASI) to assess self-reported substance use.⁸⁷ We have adapted the ASI to also assess use of illicit buprenorphine.¹³ We will report the following continuous measures in each study arm: the percentage of urine drug tests that are positive for illicit opioids (opiates, oxycodone, methadone, illicit buprenorphine), self-reported days of illicit opioid use, and percent of participants achieving *opioid abstinence*, defined as no illicit opioid use based on self-report and urine drug testing.

Principal Investigator: [name]

b.) Retention in treatment: For participants initiating BMT, we will determine whether they are retained in treatment at three and six months following initiation (dichotomous measure). We will define retention as having a medical visit and active buprenorphine prescription each month after BMT initiation. We will also determine the proportion of days following BMT initiation that participants had an active prescription in order to detect lapses in treatment (continuous measure).

c.) HIV risk behaviors: We will determine changes in drug-related HIV risks using the HIV Risk Behavior Survey – a validated, well-studied instrument that documents injection and sexual behaviors over the previous 30 days. This instrument has been studied among out-of-treatment PWID and BMT patients.^{86,93} As previously reported, we will create a dichotomous measure (yes/no) of injecting risk based on self-report of at least one risk behavior (sharing syringes, not using bleach to clean syringes, sharing cookers, or front/back loading of syringes).⁹³ Individual risk behaviors will be explored individually.

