Aim 2: Primary outcome (safety): We will use a dichotomous measure (yes/no) of **buprenorphine diversion** for all participants to determine how many sell or give away prescribed medication. We will define diversion as having at least one problem behavior over the 24 weeks: non-adherence to prescribed medication on electronic monitoring, self-reported diversion, or a urine sample consistent with diversion. Adherence will be determined weekly with Wisepill adherence for one week equaling $X/7Y$, where X = number of openings in one week and Y = number of doses prescribed per day. For the composite measure, non-adherence will be considered < 90% adherence. We will adapt the MGH Medication Questionnaire, which assesses misuse of prescribed medications, including selling medication, letting others take prescribed medication, or taking medication to get “high”. For the composite measure, self-reported diversion will be defined as an affirmative response to the question, “In the past 2 weeks, have you sold your buprenorphine to others?” We will also test each urine sample for buprenorphine, and if absent among participants prescribed BMT, the urine sample will be considered consistent with diversion. Each behavior will also be explored individually.

Aim 2: Secondary outcomes (safety): We will also report illicit buprenorphine use (i.e., buprenorphine detected in urine samples of participants who are not prescribed BMT), and determine changes in illicit buprenorphine use from baseline to study completion among participants in each study arm.

Aim 3: Primary outcome (incremental cost-effectiveness ratio, ICER): The ICER will be calculated by dividing the incremental mean cost of the O-BMT arm relative to the control arm by the incremental mean effectiveness of the O-BMT arm relative to the control arm (instruments used to measure costs and effectiveness are described in detail below). The primary economic effectiveness outcome will be the quality-adjusted life-year (QALY), a measure that incorporates both duration and health-related quality-of-life and is recommended as the primary economic effectiveness measure.⁹⁴ The QALY captures a wider range of consequences than other clinical effectiveness measures, and permits comparisons across disorders and interventions, allowing for broader economic interpretation. Also, generally accepted value thresholds have been established for QALYs, but not for clinical measures.⁹⁵

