Aim 1: To test the effectiveness of O-BMT. *H1: more participants randomized to O-BMT (vs. control) will be engaged in BMT at 30 days.* Our primary analysis will determine the effect of the intervention (O-BMT). We will use a chi square test comparing the proportion of participants in each study arm who have an active buprenorphine prescription 30 days after enrollment. We will also conduct a multivariable logistic regression adjusting for mental illness, polysubstance use, and addiction severity.

H2: Reductions in opioid use will be greater among participants randomized to O-BMT (vs. control) over 24 weeks. We will use generalized estimating equations to compare changes in opioid use between study arms over the 24 week study period. One model will use results from urine drug tests at 1, 2, 4, 6, 8, 12, and 24 weeks. A second model will compare the mean number of days (of the prior 30 days) with self-reported opioid use at 4, 8, 12, and 24 weeks.

H3: Reductions in HIV risk behaviors will be greater among participants randomized to O-BMT (vs. referral) over 24 weeks of follow-up. We will use generalized estimating equations to compare changes in injecting risk at 2, 12, and 24 weeks.

Aim 2: To test the safety of onsite buprenorphine treatment at syringe exchange programs.

H4: Diversion of buprenorphine will not be significantly greater among participants randomized to O-BMT (vs. control). By definition, participants who are not prescribed buprenorphine will not have an opportunity to divert their medication, but we will use an intention to treat approach to maintain randomization. The risk difference

Principal Investigator: [name]

threshold margin for non-inferiority will be 5%. We will construct Wald 95% confidence intervals (CIs) for a difference in diversion rates between the two arms and examine if the lower bound of the 95% CI is greater than the threshold margin. If potential confounding factors are unbalanced and require adjustment, we will apply logistic regression and estimate the Odds Ratio (OR) and its CI, examining if the lower bound of the OR is greater than the OR converted from the risk difference.

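### Urine-defined illicit buprenorphine use depends on prescription status, which O-BMT is meant to change, so urine cannot separate less street use from relabelling

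*Combined protocol and SAP*

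**What the plan says.** - **Illicit buprenorphine** (Main outcome variables, Aim 2: Secondary outcomes). The definition and the planned report read "buprenorphine detected in urine samples of participants who are not prescribed BMT), and determine changes in illicit buprenorphine use from baseline to study completion"; the change is to be given for each arm. The text gives no between-arm test, no denominator, and no window for deciding whether someone counts as prescribed when a sample is taken.
- **Illicit opioid use** (Aim 1: Secondary outcomes, item a). The urine measure is the percentage of tests "positive for illicit opioids (opiates, oxycodone, methadone, illicit buprenorphine". Abstinence combines urine with self-report. On self-report the section says: "We have adapted the ASI to also assess use of illicit buprenorphine".
- **H2 analysis** (Analysis, Aim 1). There are two models. For urine the plan says: "One model will use results from urine drug tests at 1, 2, 4, 6, 8, 12, and 24 weeks". The other takes self-reported days of opioid use over the preceding month, at weeks 4, 8, 12 and 24. The urine model does not restate its analytes, so I take them from the outcome definition above. The Aim 2 text is the only place that defines illicit buprenorphine in urine.
- **Prescription status.** The exclusions rule out agonist treatment in the 30 days before entry. H1 expects more O-BMT than referral participants to be engaged at 30 days, and engagement means an active buprenorphine prescription.

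**The concern.** At baseline nobody should be on prescribed buprenorphine, so every buprenorphine-positive urine counts as illicit. During follow-up the same result is illicit in a participant without a prescription and cannot be illicit in one with a prescription. Street use among prescribed participants becomes invisible to urine, and more participants are expected to be prescribed in one arm than in the other.

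Two readings are at stake. A larger fall from baseline in the O-BMT arm could be taken as less street use when part of it only restates H1. In the H2 urine model and in abstinence, a urine positive for buprenorphine alone counts against a participant without a prescription and not against one who has it. The population makes this relevant: the Background reports that "among 102 SEP participants, 57 had taken diverted buprenorphine, and this was most common among those with barriers to BMT".

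**Working it through.** **Plan's own figure.** The documents give no number for H2 or for illicit buprenorphine. The engagement rates used below come from D.10 Power analysis, so I checked Table 3 first. With a pooled chi-square test at 80% power and two-sided 0.05 (alpha is my assumption, as it is not stated):

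n per arm = [1.96 × √(2 × 0.245 × 0.755) + 0.8416 × √(0.16 × 0.84 + 0.33 × 0.67)]² / 0.17² = 99.3, rounded up to 100.

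The total is 200, as stated for 16% vs 33%. For 16% vs 49% the same method gives 62, also as stated.

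**Inputs**
- e, the share with a prescription: referral e0 = 16% (or 0%), O-BMT e1 = 33%, 49% or 68%, all from D.10. Using these at a urine visit is an assumption.
- b, the share of samples that are buprenorphine-positive apart from any prescribed supply, the same in both arms: assumed 10% to 30%. The Background figure of 57/102 = 56% has no stated period, so it serves only as an upper bound.
- q, the share positive for another illicit opioid: assumed 50% to 80%, independent of b.

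**Illicit-buprenorphine outcome, all participants in the denominator, street use unchanged**

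Rate = b × (1 − e). Ratio = (1 − e1)/(1 − e0). Difference = b × (e1 − e0).

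At b = 20% and 49% vs 16%: O-BMT 0.20 × 0.51 = 10.2%; referral 0.20 × 0.84 = 16.8%; difference 6.6 points. From a baseline of 20% in each arm, the falls are 9.8 and 3.2 points.

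| Referral vs O-BMT prescribed | Ratio | Difference, b = 10% to 30% | Chance of a significant result for O-BMT |
|---|---|---|---|
| 16% vs 33% | 0.67/0.84 = 0.80 | 1.7 to 5.1 points | 6.6% to 13.6% |
| 16% vs 49% | 0.51/0.84 = 0.61 | 3.3 to 9.9 points | 15% to 41% |
| 0% vs 68% | 0.32/1.00 = 0.32 | 6.8 to 20.4 points | 49% to 96% |

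The last column is for a single-visit chi-square test with 100 per arm, where 2.5% is nominal. The plan names no such test; the column shows only what an informal comparison could produce. At the upper bound b = 56% the differences are 9.5, 18.4 and 38.0 points.

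**Relabelling or substitution.** Let f be the fraction of would-be street users who keep using street buprenorphine once prescribed. The artefact at 49% vs 16% and b = 20% is f × 6.6 points, and the remaining (1 − f) × 6.6 is a real move to prescribed supply. Urine carries no information on f.

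**Denominator of unprescribed participants only.** The same model gives b in both arms and no difference. The comparison is then between groups selected after randomisation by something the intervention changes, and the direction of bias is unknown.

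**H2 urine model.** A sample positive for another illicit opioid stays positive, so only buprenorphine-only samples, s = b × (1 − q), change class. Rate = q + s × (1 − e); difference = s × (e1 − e0). Here s runs from 0.10 × 0.20 = 2% to 0.30 × 0.50 = 15%.
- 16% vs 33%: 0.3 to 2.6 points (chance of a significant result about 3% to 6%).
- 16% vs 49%: 0.02 × 0.33 = 0.7 to 0.15 × 0.33 = 5.0 points (3% to 11%).
- 0% vs 68%: 1.4 to 10.2 points (4% to 31%).

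These chances are again single-visit figures, not the operating characteristics of the seven-visit GEE.

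**Without buprenorphine.** The rate is q in both arms, and the difference is 0 in every scenario.

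**The case against.** The best defence has four parts.

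1. *Replacing street buprenorphine with treatment is a benefit.* The Background links diverted use to poor access to BMT, so a fall may be exactly what the investigators hope to see. This stands: the 6.6 points cannot be called wholly spurious. It does not make urine able to show which part is real.
2. *The outcome is descriptive.* The plan reports change within each arm, and its declared between-arm test of diversion is H4. This stands, and limits the point to how a fall is interpreted. Parallel reporting by arm still invites the comparison.
3. *Other measures cover the gap.* The ASI asks about illicit buprenorphine, abstinence needs self-report as well as urine, H2 has its own self-report model, and dispensing data are collected. This largely stands, but the plan does not say that these measures govern the illicit-buprenorphine comparison, and it plans no urine analysis without buprenorphine.
4. *Behaviour could offset the shift.* The arms would show equal rates if street use among unprescribed O-BMT participants were (1 − e0)/(1 − e1) times that in referral: 1.25, 1.65 or 3.1 in the three scenarios. That is true, but it also means that a rise of that size would be hidden.

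A reader might infer that H2 favours O-BMT by definition. The documents do not support that: three of the four analytes are unaffected by a buprenorphine prescription, and the self-report model does not use the urine rule. A reader might also infer that medication passed from O-BMT to referral participants at the same exchange would make a harm look like a benefit. Randomisation within site makes such transfer possible, but the documents give no rate for it, and the Aim 2 primary outcome looks for the donors through self-reported selling, electronic monitoring and buprenorphine-negative urines while prescribed.

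**Conclusion.** The point holds for the urine measure of illicit buprenorphine. Detection depends on a post-randomisation status that O-BMT is meant to change, and with an all-participant denominator the expected ratio under unchanged street use is 0.61 at 49% vs 16%, whatever b is. The 6.6-point figure also needs b = 20%, which is an assumption, and is the largest artefact under those inputs because it takes none of the fall as substitution. If the denominator is unprescribed participants, the fault is a different one, of unknown direction.

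For the H2 urine model the same mechanism is present but small to moderate: 0.7 to 5.0 points at 16% vs 49%, with b and q assumed and independent and the analytes carried over from the outcome definition. Abstinence is exposed through its urine component only. Everything here requires that prescription rates differ between arms. I rate it moderate for the Aim 2 secondary outcome and minor to moderate for H2. The 30-day engagement outcome and the sample of 250 are not touched.

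**What to change.** 1. Pre-specify the H2 urine model and the abstinence outcome with buprenorphine left out of the positive definition, reported beside the current definition. Claim a robust urine effect only if both agree. Which of the two is labelled main is a matter of preference, since leaving buprenorphine out also ignores genuine unprescribed use.
2. For illicit buprenorphine, base any between-arm comparison on the adapted ASI item in all randomised participants, at the visits where the ASI is given.
3. Set prescription status for each urine sample from Prescription Drug Monitoring Program dispensing within a stated window, so that a prescription written but never filled does not change the class of a sample.
4. Report the urine measure descriptively with its denominator stated. Do not present a fall from baseline as an effect of O-BMT, and do not compare arms among visits without a prescription, because that conditions on a post-randomisation status.

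The cost is SAP wording and the additional buprenorphine-free analyses, all from data already planned. The drawback is that the illicit-buprenorphine comparison would rest on self-report from participants who know their arm.

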Aim 3: Secondary outcomes (ICER, clinical) We will also calculate ICERs using the clinically meaningful effectiveness measure of duration of opioid abstinence, which will be operationalized as the proportion of the year the participant was abstinent from opioids (the *abstinent year*). The calculation of cost-per abstinent-year enables comparisons with existing economic evaluations that have utilized similar effectiveness measures.⁹⁶

Health-related quality of life: will be measured using the EuroQol 5D-5L (EQ-5D).^{90,97} Preference weights obtained from the EQ-5D will be used to calculate QALYs. The EQ-5D is the most widely used generic, preference-based health-related quality of life instrument in prospective cost-effectiveness analyses.⁹⁸

Criminal and legal activities: will be self-reported using Timeline Followback, and measured using the Criminal and Legal Activities Form. The following measures will be obtained: days involved in criminal activity; average number of crimes/day on days when illegal activity occurred; days incarcerated in any facility; specific crimes committed, and charges and convictions for those crimes; visits to parole/probation officer; and parole/probation violations.

Non-study resources: Non-study medical resources (e.g., medications, and use of inpatient, outpatient and emergency services) will be self-reported using Timeline Followback and collected using the Non-Study Resources Form. Use of non-medical resources (e.g., travel time to medical care) will also be self-reported and collected by the Non-Study Resources Form.

Intervention Resource Utilization and Costs: The resource utilization and resulting cost of implementing and administering the O-BMT intervention will be estimated using a tailored version of the Drug Abuse Version 6-25-20

Principal Investigator: [name]

Treatment Cost Analysis Program (DATCAP) instrument.^{99,100} The DATCAP is a standardized, customizable tool used to estimate costs of addiction treatment programs in diverse settings.

Other covariates: We will measure factors that may be associated with BMT outcomes, including sociodemographic characteristics, insurance status, depressive symptoms, motivation for treatment, and prior buprenorphine exposure. We will also measure other outcomes that are important for clinical care, including self-efficacy, perceived discrimination in medical care, and treatment satisfaction.

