Data management. Urine drug tests will be conducted at the syringe exchange program or CHC and will be entered onto a paper Case Report Form and then entered into a password protected database. The entry will be verified by another staff member. Interviews using REDcap surveys allow for direct data entry by study participants. To ensure confidentiality, participant identifiers will not be recorded on interviews or other data forms. Instead, participants will be assigned a unique study ID that will be used on all data documents and in databases. Participant's names and consent forms will be stored separately from research data in locked file cabinets. Electronic data will be stored in a password-protected server, which will be back up daily and can only be accessed by the research team. Because we will be collecting data on buprenorphine diversion, we also received a Certificate of Confidentiality from NIDA to provide additional protection of confidentiality (see Human Subjects for details).

Analysis: All primary analyses will be intention to treat, including participants who are lost to follow-up. In secondary analyses, we will conduct per-protocol analyses to ascertain outcomes among participants who actually initiate BMT at the SEP or CHC. We will conduct additional exploratory analyses on a per-protocol basis to further assess outcomes (e.g., satisfaction with buprenorphine treatment)

Preliminary analyses. We will first review and summarize data using descriptive summaries and graphical analyses to ensure that reported values are within appropriate ranges, to check for the presence of outliers and abnormal values, and to verify that the distributions of measures meet the assumptions of the statistical tests that are planned as described below.

Missing data. For missing categorical data, we will use multivariate multiple imputation using the fully conditional specification method.¹⁰¹ We will repeat imputations 20 times, and then we will compare statistical results using datasets that include imputed values and the dataset that drops missing values. This will guide our interpretation of our assessment of the impact of missing data on our study findings, as well as our interpretation of overall results.

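### Imputation is specified only for categorical data: opioid-use days and interview-based economic inputs have no stated missing-data method, and urine results have no missing-not-at-random sensitivity analysis

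*Combined protocol and SAP*

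**What the plan says.** The Missing data paragraph under Analysis is the only missing-data text in the combined protocol and SAP. Its scope is "For missing categorical data, we will use multivariate multiple imputation using the fully conditional specification method". It continues "We will repeat imputations 20 times", after which "we will compare statistical results using datasets that include imputed values and the dataset that drops missing values". That comparison is meant to inform how the team reads the effect of missing data. The paragraph does not say which of the two results is the main one.

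The Analysis section opens with "All primary analyses will be intention to treat, including participants who are lost to follow-up".

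H2 has two GEE models. For the first, "One model will use results from urine drug tests at 1, 2, 4, 6, 8, 12, and 24 weeks". For the other, "A second model will compare the mean number of days (of the prior 30 days) with self-reported opioid use", at weeks 4, 8, 12 and 24. For Aim 3, "Preference weights obtained from the EQ-5D will be used to calculate QALYs". The Aim 3 analysis text fits generalized linear models to costs, preference weights and abstinent days. It attaches no missing-data rule to them, and its sensitivity analyses are described without mention of missing data.

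**The concern.** Opioid-use days, EQ-5D weights and resource use are not categorical, so as worded the imputation does not reach them. They come from interviews, and a missed research visit loses them along with the urine sample. The power analysis allows 20% attrition, and the group's earlier studies kept 84% of participants over six months. Active drug use is a plausible reason for missing a visit. Allocation is open and the arms start treatment in different places, so missingness could also differ by arm.

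Two things are at stake. First, the promise to include people lost to follow-up has no mechanism for the continuous outcomes. An unweighted GEE on available data can be biased if dropout depends on earlier use. Second, the urine analysis has no step showing how far the H2 conclusion depends on what the missing samples would have shown.

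**Working it through.** **1. The plan's own figure.** The attrition allowance belongs to the power analysis: 250 enrolled, 200 after 20% loss, at least 80% power for engagement. The most demanding scenario is 16% vs 33%. Alpha is not stated; I assume two-sided 0.05 and a pooled chi-square test.

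- Mean proportion: (0.16 + 0.33)/2 = 0.245.
- n per arm = [1.96·√(2·0.245·0.755) + 0.8416·√(0.16·0.84 + 0.33·0.67)]² / 0.17² = (1.192 + 0.502)² / 0.0289 ≈ 99.3, so 100 per arm and 200 in total.
- Power at 100 per arm is 80.3%, and 200/(1 − 0.20) = 250.

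The figure reproduces. It concerns the primary outcome; the documents give no expected missingness for urines or interviews.

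**2. What the imputation text reaches.**

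| Quantity | Type | Source | Missing-data method |
|---|---|---|---|
| Engagement at 30 days (H1) | categorical | clinic records, state prescription monitoring | within scope; little exposed to missed visits |
| Urine results (H2, first model) | categorical | research visits | imputation, compared with complete cases |
| Opioid-use days (H2, second model) | continuous | interview | none stated |
| EQ-5D weights | continuous | interview | none stated |
| Abstinent days | continuous | interview and urine | none stated |
| Self-reported resource use, criminal-justice activity | mainly counts | interview | none stated |
| O-BMT intervention cost | continuous | DATCAP | not dependent on participant follow-up |

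**3. Illustrative size for urines, complete-case analysis.** All rates are assumed. Let m be the proportion missing in an arm, q the positive rate among missing samples, and 50% the positive rate among observed samples in both arms. The full rate is (1 − m)·0.5 + m·q, so the error in the arm difference is (difference in m)·(q − 0.5).

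| Missing, by arm | q | Full rates | Error |
|---|---|---|---|
| 15% vs 25% | 0.8 | 54.5% vs 57.5% | 3 points |
| 15% vs 25% | 1.0 | 57.5% vs 62.5% | 5 points |
| 10% vs 30% | 0.8 | 53.0% vs 59.0% | 6 points |
| 10% vs 30% | 1.0 | 55.0% vs 65.0% | 10 points |

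With equal missingness and the same q in both arms, the error in this setting is zero.

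**4. What the planned comparison can show.** I simulated 300 trials of 125 per arm at a single visit, with 20 imputations from a model containing arm and the previous urine. Missingness depended on the unseen result. Mean risk differences (O-BMT minus referral), in points:

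| Probability of being missing (O-BMT / referral) | Full data | Complete case | Imputed |
|---|---|---|---|
| positives 15% / 35%; negatives 10% / 5% | −10.3 | −3.1 | −3.2 |
| positives 35% / 15%; negatives 5% / 10% | −9.8 | −18.1 | −17.9 |
| positives 25% / 25%; negatives 8% / 8% | −9.8 | −10.1 | −10.1 |

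In the first two rows the two analyses agree within 0.2 points, while both miss the full-data difference by 7 to 8 points. In the third, where the mechanism is the same in both arms, the error is 0.3 points.

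**5. What a sensitivity analysis would add.** Assume observed positive rates of 50% (O-BMT) and 65% (referral), a difference of −15.0 points. Counting missing as positive gives:

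- 20% missing in each arm: (0.20 + 0.80·0.50) − (0.20 + 0.80·0.65) = −12.0 points.
- 10% / 30% missing: 0.550 − 0.755 = −20.5 points.
- 30% / 10% missing: 0.650 − 0.685 = −3.5 points.

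With 20% missing in each arm, the extreme bounds run from 0.40 − 0.72 = −32.0 to 0.60 − 0.52 = +8.0 points.

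**The case against.** The other side has several sound points.

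- A reader might infer that imputation, like complete-case analysis, treats missing visits as resembling observed ones. It does not: it conditions on observed data. A gap between the two results would signal missingness related to observed variables, so the comparison is informative and worth keeping.
- A reader might also infer that the plan takes agreement as proof that missing data do no harm. The text says only that the comparison will inform interpretation.
- Missingness that depends on unseen results cannot be detected from observed data by any method. A tipping-point analysis measures sensitivity; it does not detect the mechanism. This is a robustness gap, not an error.
- The absence of a method for continuous data is read from silence. The title of the cited imputation paper covers discrete and continuous data, so the restriction may be a drafting slip. EQ-5D item responses are categorical and could be imputed. The multivariable GLMs and recycled predictions partly address missingness related to their covariates.
- Not all Aim 3 costs are exposed: intervention costs come from DATCAP, and prescriptions and clinic visits from records.
- Counting missing as positive is itself a strong assumption, as step 5 shows.

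These points narrow the concern. They do not remove it: the current wording is restrictive, item-level EQ-5D imputation is not stated, the GLMs are fitted to observed values with no list of covariates, and no missing-not-at-random analysis appears for urines.

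**Conclusion.** The point holds for secondary and economic outcomes. Opioid-use days and the interview-based Aim 3 inputs have no stated missing-data method. This matters most for the QALY-based cost-effectiveness ratio, the primary Aim 3 outcome. For urines, the planned comparison addresses missingness explained by observed variables but says nothing about sensitivity to missingness that depends on the result.

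The size is unknown. The 3 to 10 points describe a complete-case difference under assumed missingness differing by 10 to 20 points between arms and 80-100% positivity among missing samples. They do not measure the planned imputed analysis, and no figure can be given for opioid-use days, EQ-5D or costs. The simulated 7 to 8 points likewise require a mechanism that differs by arm.

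A reader might infer that the trial's main result is at risk. The documents do not support that: an active prescription at day 30 is read from clinic records and the state monitoring program, so it is largely unaffected.

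**What to change.** Amend the Missing data paragraph before analysis:

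1. Extend the fully conditional imputation to opioid-use days, EQ-5D (stating whether items or weights are imputed) and self-reported resource use, including criminal-justice activity. Put arm, site and earlier values in the imputation model. Say how abstinent days are derived from imputed data.
2. Name the imputed analysis as the main one for these outcomes.
3. Keep the complete-case comparison as a supplement.
4. Add a missing-not-at-random sensitivity analysis for the H2 urine model: a tipping point in which the positive rate among missing samples varies separately by arm, with missing counted as positive as one scenario. Report missingness by arm and visit beside it.

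Step 1 still assumes that missingness depends only on observed data; the amended text should say so. The cost is SAP wording and modest extra analysis work, including combining imputation with the bootstrap in Aim 3. It needs no new data, visits or participants.
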